2.0 TRIAL DESIGN

2.1 Trial Design

This is a Phase I/Ib investigator-initiated open label trial of the combination of VESANOID and pembrolizumab treatment.

A total of 24 evaluable patients will be recruited into the study. All the patients will receive 200mg Q3W pembrolizumab treatment plus the supplemental treatment of 150 mg/m² VESANOID orally for 3 days surrounding each of the first four infusions of pembrolizumab (day -1, day 0, day +1) for a total of 12 days of VESANOID treatment (Section 2.2 *Trial Schema/Diagram*).

To closely monitor DLTs, subjects will be recruited into the study using a cohort size of 6. The toxicity monitoring design is to inform de-escalation decisions based on safety if needed. DLTs will be assessed during the DLT assessment window of 21 days following the first dose of Vesanoid and Pembrolizumab (Cycle 1 Day 0 to Cycle 2 Day 0). Patients who withdraw from the study prior to completing the DLT assessment window for any reason other than a DLT will be replaced. See Section 6.1.1.2.3 for DLT definition.

After the first 6 subjects in cohort 1 complete the DLT period, the Sponsor-Investigator will review data pertaining to the dose de-escalation decision. Available adverse event data and laboratory assessments will be used to determine whether the Vesanoid dose should be continued at 150 mg/m^2 or whether the Vesanoid dose should be de-escalated to 100 mg/m^2 in the subsequent six subjects to be enrolled in cohort 2.

Dose de-escalation will proceed in accordance with the following rules:

- 6 patients will be treated in cohort 1.
 - If 0-2 patients experience a DLT in cohort 1, the Vesanoid dose will be maintained.
 - \circ If \geq 3 patients in cohort 1 experience a DLT, then dose de-escalation of Vesanoid will proceed.
- 6 additional patients will be treated in cohort 2 at either the starting Vesanoid dose (150 mg/m²) or the reduced Vesanoid dose (100 mg/m²).
 - If 0-2 patients experience a DLT in cohort 2, the Vesanoid dose will be maintained.
 - If \geq 3 patients in cohort 2 experience a DLT, then the study will stop.
- If it is determined that the dose will be maintained from Cohort 2, then an additional cohort (cohort 3) of up to 12 patients (depending on the number of patients required to achieve the enrollment goal of 24 patients, but not to exceed 30 patients) will be treated at either the starting Vesanoid dose (150 mg/m²), or the reduced Vesanoid dose (100 mg/m²).

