2.2 Trial Schema/Diagram

Proposed schedule for treatment and blood draws.

Figure 1. Diagram of the treatment and blood draw schedule for this study. Patients will receive pembrolizumab infusions every three weeks. Patients will also receive 3 days of VESANOID treatment surrounding each of the first 4 infusions of pembrolizumab, beginning one day prior to the infusion (a total of 12 days of VESANOID). Six tubes of peripheral blood (for a total of approximately 40 ml) will be drawn at enrollment, at the 2rd and 4th infusions, and within 60 days of the final VESANOID dose for additional functional experiments.

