4.1.2 Preclinical and Clinical Trial Data

Pre-clinical data suggest that VESANOID abrogates the suppressive effects of MDSCs isolated from both human cancer patients and mouse cancer models in vitro (14-16). Furthermore, mice treated with VESANOID have decreased frequencies of MDSCs and increased frequencies of dendritic cells that improve T cell responses against tumors (17-19).

Our preliminary research has identified a population of immunosuppressive MDSCs (Lineage negative, HLA-DR negative, CD11b positive, and CD33 positive) that are increased in Stage IV melanoma patients relative to healthy donors. To establish MDSCs as a potentially important contributor to immunosuppression in melanoma patients, we compared the frequency and function of immunosuppressive MDSCs in the peripheral blood of healthy donors, Stage I, and Stage IV melanoma patients (10). We found significant increases in the frequency of MDSCs in the peripheral blood of Stage IV

melanoma patients compared to healthy donors. We showed that the frequency of these cells correlates with an increase in regulatory T cells and an increased level of IL-6 and IL-8 cytokines in the peripheral blood. Furthermore, patients with clinical disease progression had an increased frequency of these cells. We also found that patients with a high frequency of MDSCs had decreased overall survival and an increased risk of death (hazard ratio 4.83, p = 0.016). This increased risk of death was independent of other clinical factors including age, gender, and treatment regimens. Finally, we demonstrated that MDSCs isolated from Stage IV melanoma patients were significantly more immunosuppressive than those isolated from healthy donors. Overall, these data suggest that MDSCs may be a significant contributor to immunosuppression in melanoma patients and that targeting these cells in a combinatorial approach may improve immune responses against melanoma.

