4.2 Rationale

4.2.1 Rationale for the Trial and Selected Subject Population

Reducing immunosuppression by MDSCs during pembrolizumab treatment may maximize T cell activation and expansion, increasing the overall effectiveness and success of pembrolizumab treatment. This pilot clinical trial will demonstrate whether combinatorial immunotherapeutic approaches that target immunosuppressive MDSC's can augment tumor-specific T cells and benefit melanoma patients.

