Tcell subsets (CD4, CD8, Treg) and MDSC subsets (CD14+, CD15+) will be analyzed by flow cytometry at each of the blood draws time points and compared to whole blood cells, total lymphocytes and monocytes populations between time points and compared between pretreatment, on treatment and post treatment. T cell activation will be assessed by CD107 and IFNg production in response to PMA and ionomycin and compared between pretreatment, on treatment. MDSC functional assays will assess the ability of MDSC's to suppress stimulated T cell proliferation as a percent of positive control and will be compared between time points and compared between the points and compared

Linear mixed effects models will be used to assess the frequency of MDSC subsets over times. Contrast statements will be used to estimate changes in the frequency of MDSC subsets and its suppressive function from baseline after treatment at different time points. For PFS endpoint, Kaplan-Meier (KM) curves and median estimates from the KM curves will be provided as appropriate. Subjects without efficacy evaluation data or without survival data will be censored at Day 1. The change in frequency of T cell subsets, the expression of activation markers, and the CTL response will be evaluated using paired t-test. Correlations between the frequencies of MDSCs and T cell subsets or expression of activation markers will be evaluated using Pearson or Spearman Correlation Coefficients at a specified time points. Alternatively, Intraclass correlation coefficients will be used to assess the potential correlations among those measurements over time.

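### The SAP names an intraclass correlation, with no form or scaling, to relate MDSC to T-cell measures over time; its value would depend on scale and form and could not be read as association

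*Combined protocol and SAP*

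**What the plan says.** The efficacy part of Section 8.0 gives each immune measure its own method.

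- MDSC over time: "Linear mixed effects models will be used to assess the frequency of MDSC subsets over times". Contrasts then estimate change from baseline in frequency and in suppressive function.
- T-cell subsets, activation markers and the CTL response: change is tested with a paired t-test.
- The link between the two: "Correlations between the frequencies of MDSCs and T cell subsets or expression of activation markers will be evaluated using Pearson or Spearman Correlation Coefficients", at specified time points. The next sentence reads "Alternatively, Intraclass correlation coefficients will be used to assess the potential correlations among those measurements over time".

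The SAP does not say which ICC is meant, whether the markers would first be put on a common scale, or when the ICC would replace Pearson or Spearman. The markers in scope are wide: "Tcell subsets (CD4, CD8, Treg) and MDSC subsets (CD14+, CD15+) will be analyzed by flow cytometry". Section 2.1 sets the number of patients ("A total of 24 evaluable patients will be recruited into the study"), and Section 2.2 the sampling: blood "will be drawn at enrollment, at the 2rd and 4th infusions, and within 60 days of the final VESANOID dose", which makes four draws per patient.

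**The concern.** On the plain reading, the measurements in the ICC sentence are the MDSC and T-cell measures named in the sentence before it. The ICC is then the only method in the SAP for relating the two over time. Pearson and Spearman are tied to single time points, the mixed model covers MDSC outcomes alone, and the paired t-test covers T-cell change alone.

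An ICC describes how alike repeated measurements of the same quantity are. Applied to two different quantities, it responds to the gap between their means and to unequal variances as well as to whether they move together.

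Direction matters here. Section 4.2.1 gives the rationale: "Reducing immunosuppression by MDSCs during pembrolizumab treatment may maximize T cell activation and expansion". That implies an inverse relation between MDSC and T-cell activation. For regulatory T cells, Section 4.1.2 points the other way: "We showed that the frequency of these cells correlates with an increase in regulatory T cells". The over-time method therefore has to tell a negative association from a positive one. At stake is the readability of one correlative result.

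**Working it through.** **Inputs.** From the documents: 24 patients (Section 2.1) and 4 draws each (Section 2.2). The documents give no marker means, SDs, target correlation or ICC form, so there is no figure of the plan's own to reproduce. Assumed for illustration: MDSC mean 5, SD 2, with T cells at (a) mean 30, SD 8, (b) mean 10, SD 4, or (c) the same mean and SD as MDSC. True correlation r = -0.6, 0, +0.6.

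**Formulas** (two markers, large-sample values; d = difference in means, s1 and s2 = SDs):

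- One-way ICC = (2·r·s1·s2 - d²/2) / (s1² + s2² + d²/2)
- Absolute-agreement ICC = 2·r·s1·s2 / (s1² + s2² + d²)
- Consistency ICC = 2·r·s1·s2 / (s1² + s2²)

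The mean difference d enters the first two. The SDs enter all three. All three equal r only when d = 0 and s1 = s2.

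**Scenario (a):** d² = 625, s1² + s2² = 4 + 64 = 68, and 2·r·s1·s2 = ±19.2 at r = ±0.6.

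- One-way: (-19.2 - 312.5)/380.5 = -0.87; -312.5/380.5 = -0.82; (19.2 - 312.5)/380.5 = -0.77
- Absolute agreement: ±19.2/693 = ±0.03
- Consistency: ±19.2/68 = ±0.28

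**Scenario (b):** d² = 25, s1² + s2² = 4 + 16 = 20, and 2·r·s1·s2 = ±9.6.

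- One-way: -22.1/32.5 = -0.68; -12.5/32.5 = -0.38; -2.9/32.5 = -0.09
- Absolute agreement: ±9.6/45 = ±0.21
- Consistency: ±9.6/20 = ±0.48

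**Simulation check** (2,000 datasets per setting, 24 patients by 4 draws, pairs pooled over draws):

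| Scenario | Measure | r = -0.6 | r = 0 | r = +0.6 |
|---|---|---|---|---|
| (a) | One-way ICC | -0.87 | -0.82 | -0.77 |
| (a) | Absolute agreement | -0.03 | 0.00 | +0.03 |
| (a) | Consistency | -0.28 | 0.00 | +0.28 |
| (b) | One-way ICC | -0.68 | -0.38 | -0.09 |
| (b) | Absolute agreement | -0.22 | 0.00 | +0.21 |
| (b) | Consistency | -0.48 | 0.00 | +0.48 |
| (c) | All three forms | about -0.60 | about 0 | about +0.60 |
| all | Repeated-measures correlation | -0.60 | 0.00 | +0.60 |

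The simulation agrees with the formulas to within 0.01. In (a) and (b) the one-way form is negative even when the true relation is positive. In (a) the absolute-agreement form is close to zero at every r. The consistency form keeps the sign but shrinks the size.

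**Does standardising rescue the ICC?** For independent pairs, largely yes: on z-scored data it nearly equals Pearson r. With four draws pooled per patient it need not. If half of each marker's variance is stable between-patient variation unrelated to the other marker (assumed), the pooled correlation is 0.5·0 + 0.5·(±0.6) = ±0.30. Simulation gives about ±0.30 for all three z-scored ICCs, while the repeated-measures correlation still returns ±0.60.

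**Bounds.** An analysis-of-variance ICC over k measurements cannot fall below -1/(k - 1): -1 for k = 2, -0.33 for k = 4 and -0.14 for k = 8. An ICC defined as a variance ratio from a random-intercept model cannot fall below 0.

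**The case against.** Four counter-arguments deserve weight.

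1. *An ICC can be negative.* A reader might infer that an ICC can never show an inverse relation, or that the result would be empty whatever the truth. The documents do not support that, because they leave the form open. The consistency form keeps the sign, and with equal means and SDs all three forms track the true value. Only the variance-ratio form is barred from negative values.

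2. *The ICC is an alternative.* Pearson and Spearman come first and can show an inverse relation at a time point. This stands, and it limits the concern to the over-time analysis.

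3. *The link is not a listed objective, and no sign is stated.* A reader might infer that the trial's main mechanistic result is at risk, with one inverse relation expected throughout. Section 3 does not list an MDSC-to-T-cell correlation among its objectives. The SAP states no expected direction, and Section 4.1.2 suggests a positive one for regulatory T cells. This stands as to impact.

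4. *The sentence may mean each marker's own repeated values.* An ICC would then be legitimate. The reading is possible but fits poorly with the preceding sentence and with the word that introduces the alternative. The fix should allow for it.

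The figures also rest on invented means and SDs. Their size moves with those inputs, as (a) to (c) show, and that dependence on scale is the defect.

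**Conclusion.** The concern holds in limited form. As written, the SAP offers an unspecified ICC as its over-time measure of association between different markers. Its value would depend on the form chosen and on the raw scales. At a true correlation of +0.6, the three forms run from -0.77 to +0.28 in scenario (a) and from -0.09 to +0.48 in (b), and agree near +0.60 only when means and SDs are equal. Such a result cannot be read as strength of association and, for some forms, not as direction.

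This rests on the plain reading of the sentence and on the two markers differing in mean or variance. The time-point correlations, the MDSC mixed models, the T-cell paired tests, the sample size and the primary MTD/RP2D objective are untouched. It is a minor correction, worth making before the immune data are analysed.

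**What to change.** Replace the ICC sentence in Section 8.0 with a repeated-measures (within-patient) correlation, or a bivariate linear mixed model for each MDSC and T-cell pair, over the four draws. Give confidence intervals that account for clustering by patient; resampling whole patients is one way. If the ICC was intended only for the stability of each marker over time, say so and name the form. Either change costs one SAP sentence and needs no new samples, visits or patients.

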9.0 LABELING, PACKAGING, STORAGE AND RETURN OF CLINICAL SUPPLIES

9.1 Investigational Product

VESANOID will be supplied through the University of Colorado Cancer Center's investigational pharmacy. VERSANOID is supplied as 10 mg capsules, two-tone (lengthwise), orange-yellow and reddish-brown and imprinted VERSANOID 10 ROCHE. It is packaged in high-density polyethylene opaque bottles of 100 capsule with child-resistance closure.

Pembrolizumab (200mg dosing Q3 weeks) will be supplied by Merck.

9.2 Packaging and Labeling Information

Clinical supplies will be affixed with a clinical label in accordance with regulatory requirements.

9.3 Clinical Supplies Disclosure

This trial is open-label; therefore, the subject, the trial site personnel, the Sponsor-Investigator, and/or designee are not blinded to treatment. Drug identity (name, strength) is included in the label text; random code/disclosure envelopes or lists are not provided.

9.4 Storage and Handling Requirements

Clinical supplies must be stored in a secure, limited-access location under the storage conditions specified on the label.

Receipt and dispensing of trial medication must be recorded by an authorized person at the trial site.

Clinical supplies may not be used for any purpose other than that stated in the protocol.

9.5 Returns and Reconciliation

The Sponsor-Investigator is responsible for keeping accurate records of the clinical supplies received from Merck or designee, the amount of VESANOID and Pembrolizumab dispensed to and returned by the subjects and the amount remaining at the conclusion of the trial.

Upon completion or termination of the study, all unused and/or partially used investigational product (study drug) will be destroyed at the site per institutional policy. It is the Sponsor-Investigator's responsibility to arrange for disposal of all empty containers, provided that procedures for proper disposal have been established according to applicable federal, state, local and institutional guidelines and procedures, and provided that appropriate records of disposal are kept.

10.0 ADMINISTRATIVE AND REGULATORY DETAILS

10.1 Ethics and Protection of Human Subjects

10.1.1 Ethical Standard

The PI will ensure that this study is conducted in full conformity with regulations for the Protection of Human Subjects of Research codified in 45 CFR Part 46, 21 CFR Part 50, 21 CFR Part 56. ICH E6 may also be followed to the extent it has been adopted by and is in accordance with FDA regulations.

10.1.2 Institutional Review Board (IRB)

The protocol, informed consent form(s), recruitment materials, and all subject materials will be submitted to the Colorado Multiple Institutional Review Board (COMIRB) for review and approval. Approval of both the protocol and the consent form must be obtained before any subject is enrolled. Any amendment to the protocol will require review and approval by COMIRB before the changes are implemented to the study. All changes to the consent form will COMIRB-approved.

10.1.3 Informed Consent Process

10.1.3.1 Informed Consent Form(s) (ICF)

Informed Consent Form(s) (ICF) describing in detail the study drug, study procedures, and risks are given to the subject and written documentation of informed consent is required prior to starting intervention/ administering study drug.

10.1.3.2 Informed Consent Procedures and Documentation

The informed consent process will be initiated prior to the individual's agreeing to participate in the study and continues throughout the subject's study participation. Extensive discussion of risks and possible benefits of participation will be provided to the subjects and their families.

ICFs will be IRB-approved and the subject will be asked to read and review the document. The investigator, or qualified research study personnel, will explain the clinical trial to the subject and answer any questions that may arise. All subjects will receive a verbal explanation in terms suited to their comprehension of the purposes, procedures, and potential risks of the study and of their rights as research subjects. Subjects will have the opportunity to carefully review the written consent form and ask questions prior to signing. The subjects will have the opportunity to discuss the study with their surrogates or think about it prior to agreeing to participate. The subject will sign the informed consent document prior to any procedures being done specifically for the study.

The subjects may withdraw consent at any time throughout the course of the trial. A copy of the informed consent document will be given to the subjects for their records. The rights and welfare of the subjects will be protected by emphasizing to them that the quality of their medical care will not be adversely affected if they decline to participate in this study.

The study allows the inclusion of non-English speaking and non-reading subjects. Witnesses to these consent processes will be individuals not associated with the trial and will not have a conflict of interest.

10.1.4 Subject and Data Confidentiality

Subject confidentiality is strictly held in trust by the Sponsor-Investigator, their staff, and their agents. This confidentiality is extended to cover testing of biological samples and genetic tests in addition to the clinical information relating to subjects. Therefore, the study protocol, documentation, data, and all other information generated will be held in strict confidence. No information concerning the study or the data will be released to any unauthorized third party without prior written approval of the Sponsor-Investigator.

The study monitor, other authorized representatives of the Sponsor-Investigator, representatives of the IRB or pharmaceutical company supplying study product or funding may inspect all documents and records required to be maintained by the investigator, including but not limited to, medical records (office, clinic, or hospital) and pharmacy records for the subjects in this study. The clinical study site will permit access to such records.

The study subject's contact information will be securely stored at the clinical site for internal use during the study. At the end of the study, all records will continue to be kept in a secure location for as long a period as dictated by local IRB and Institutional regulations.

Study subject research data, which is for purposes of statistical analysis and scientific reporting, will be transmitted to and stored at the University of Colorado Cancer Center. This will not include the subject's contact or identifying information. Rather, individual subjects and their research data will be identified by a unique study identification number. The study data entry and study management systems used by the University of Colorado Cancer Center research staff will be secured and password protected. At the end of the study, all study databases will be de-identified and archived at the University of Colorado Cancer Center.

10.1.5 Future Use of Stored Specimens

Any remaining specimens will be banked for future studies.

10.2 Data Management and Record Keeping

10.2.1 Clinical Data Collection and Management Responsibilities:

Clinical data collection is the responsibility of the site's clinical trial staff under the supervision of the PI. The PI is responsible for ensuring the accuracy, completeness, legibility, and timeliness of the data reported.

Clinical data will be collected during each visit by the clinical provider and stored in a locked office or cabinet with access limited to the study coordinator and/or data manager. Age, gender, pathologic features of the melanoma, co-morbid conditions, and concomitant medications will be recorded.

All paper form source documents will be recorded neatly and legibly to ensure accurate interpretation of data. When making changes or corrections, cross out the original entry with a single line, and initial and date the change. DO NOT ERASE, OVERWRITE, OR USE CORRECTION FLUID OR TAPE ON THE ORIGINAL. Clinical data will be used for the initial recording of clinical data. Corrections will be made legibly, initialed, and dated. Correction fluid and covering labels will not be used. Data quality will be monitored by random inspection of the completed forms by a research assistant and any problems will be discussed with the PI.

10.2.2 Database:

Study data will be collected and managed using OnCore. OnCore is a secure web application designed to support data capture for research studies, providing user-friendly web-based case report forms, real-time data entry validation (e.g. for data types and range checks), audit trails and a de-identified data export mechanism to common statistical packages.

The database will be designed and maintained by the University of Colorado Cancer Center Clinical Protocol and Data Management (CPDM) team. The study/data coordinator will enter the data at the conclusion of each clinic visit.

10.2.3 Study Records Retention:

Study documents will be retained per applicable regulations, and/or institution policies. No records will be destroyed without the written consent of the Sponsor-Investigator, if applicable. It is the responsibility of the Sponsor-Investigator to determine when these documents no longer need to be retained.

